3. INTERIM ANALYSES, FINAL ANALYSES AND UNBLINDING

The interim analyses could be performed after the enrollment of 15 patients is completed and 4 or more DMR responders are observed in the Expansion Cohort of LDAC combination for efficacy (Unfit Patients). In this interim analysis, the statistical test for the primary endpoint of this cohort will not be conducted and the achievement of at least 4 DMR responders in 15 patients of this cohort will be confirmed. The other analyses required at the interim analysis will be conducted according to this SAP.

The primary analysis will be performed after disease assessment on Cycle 9/Day 1 for the last (15th) patient treated in Expansion Cohort of LDAC combination for efficacy (Unfit Patients). The timing of the primary analysis is estimated to be after approximately 19 months after the first dose for the first patient in Expansion Cohort of LDAC combination for efficacy (Unfit Patients), assuming the enroll speed as 15 patients per year. The final analysis will be performed after all patients have died or 2 years after the first dose for the last patient treated, whichever occurs first. Further analyses could be performed, if necessary.

Unblinding is not applicable, as this is an open-label study.

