Treatment with the study drug combination should be continued beyond 6 cycles of treatment until objective disease progression or relapse (unless according to the Investigator there is reasonable evidence of clinical benefit, eg, HI [hematologic improvement], to justify continuation on treatment following agreement between the Investigator and Sponsor), death, unacceptable toxicity, or patient refusal (whichever is first). All patients will be followed for survival every 12 weeks up to 3 years from the first dose of the last patient enrolled in the study, or until death, end of the study, or patient withdrawal of consent, whichever comes first, regardless of initiation of new cancer therapy.

Continuation Cohort (Monotherapy Cohort):

[figure not shown]
PF-04449913 at the same dose as the patient was taking in Study B1371013 will be orally administered once daily continuously as a single agent over 28 day cycles in 1 Japanese MF patient who has been treated in Study B1371013 and without documented objective progression of disease and with continuous clinical benefit at the time the patient discontinued from Study B1371013.

In this cohort, the patient receiving PF-04449913 will continue to receive study treatment until the time of disease progression, unacceptable toxicity, death, withdrawal of consent or termination of the study by Sponsor, whichever comes first. The patient may continue PF-04449913 treatment after objective progression of disease has been determined if the patient continues to experience clinical benefit, in the opinion of the investigator, and following discussion with the Sponsor.

Figure 1. Schematic of Study Design

*intermediate or lower doses may be tested at any time during the study

SCHEDULE OF ACTIVITIES

The Schedule of Activities table provides an overview of the protocol visits and procedures. The Assessments section of the protocol contains detailed information relating to each assessment required for compliance with the protocol.

The investigator may schedule visits (unplanned visits) in addition to those listed in the Schedule of Activities table as necessary, in order to conduct evaluations or assessments required to ensure patient well-being and safety.

Table 1. Monotherapy Cohort: Single-Agent PF-04449913 in Select Hematologic Malignancies

Protocol Activity	Screening	Lead-in PK Period ¹⁴	Cycle 1 (28-day Cycle)					Even-Numbered Cycles*		Odd-Numbered Cycles*		End of Txt/Withdrawal	Post-Txt Follow-Up ¹⁸

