A total of 15 patients will be treated in this cohort and DMR rate will be evaluated. Treatment with PF-04449913 in combination with LDAC may continue until disease progression or relapse, patient refusal, or unacceptable toxicity occurs (whichever is first). All patients will be followed for survival every 8 weeks up to 2 years from the first dose of the last patient enrolled in the study, or until death, end of the study, or patient withdrawal of consent, whichever comes first, regardless of initiation of new cancer therapy (follow-up on survival status will no longer be required after Protocol Amendment 8).

Combination Cohort 2 (Fit Patients):

In this cohort, patients defined as “fit for intensive chemotherapy” based on pre-defined criteria (See Inclusion Criteria) will receive PF-04449913 once daily continuously in combination with daunorubicin and cytarabine during induction and consolidation. For the first induction cycle only, PF-04449913 will commence on Day -3 and will then be given once daily continuously for the duration of treatment. Following completion of induction and consolidation, single-agent PF-04449913 may be given to eligible patients as maintenance therapy for a maximum of 6 cycles.

A total of 6 patients will be treated in this cohort and followed up for DLT evaluation. If ≤ 1 of the 6 patients experiences a DLT event by the end of Induction Cycle 1, the tolerability of the combination will be confirmed. If 2 or more of the 6 patients experience a DLT by the end of Induction Cycle 1, additional lower dose levels may be tested using identical criteria to those outlined above with respect to DLT events.

Treatment will continue until disease progression or relapse, patient refusal, or unacceptable toxicity (whichever is first). Fit patients who complete induction, consolidation and 6 cycles of maintenance with PF-04449913 will be deemed to have completed the study treatment. However, patients who complete the 6 cycles of maintenance and demonstrate clinical benefit with manageable toxicity, and are willing to continue receiving single-agent PF-04449913, may be given the opportunity to do so following agreement between the Investigator and Sponsor, and pending study drug availability. If treatment continues beyond 6 cycles of maintenance, study procedures should continue to be performed as listed in [Table 4](#) (Schedule of Activities).

Combination Cohort 3 (Azacitidine Combination):

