In this cohort, patients with previously untreated AML and eligible for non-intensive chemotherapy will receive PF-04449913 once daily continuously at the starting dose of 100 mg in combination with azacitidine over 28 day cycles.

A total of 6 patients will be treated in this cohort and followed up for DLT evaluation. The DLT evaluation period includes the first cycle of treatment. If ≤ 1 of the 6 patients experiences a DLT by the end of Cycle 1, the tolerability of the combination will be deemed confirmed. If 2 or more of the 6 patients experience a DLT by the end of Cycle 1, the investigator and the sponsor will review all available safety data and discuss the next steps.

Since responses to azacitidine may require 4-6 cycles of administration to emerge, treatment with the study drug combination should be continued for at least 6 cycles, or until death, unacceptable toxicity, or patient refusal (whichever is first). If documentation of disease progression occurs within the first 6 cycles of study treatment, the patient **SHOULD NOT** be withdrawn from study treatment following agreement between the Investigator and Sponsor if, in the Investigator's judgment, the patient is still likely to receive clinical benefit.

[figure not shown]
Treatment with the study drug combination should be continued beyond 6 cycles of treatment until objective disease progression or relapse (unless according to the Investigator there is reasonable evidence of clinical benefit, eg, HI [hematologic improvement], to justify continuation on treatment following agreement between the Investigator and Sponsor), death, unacceptable toxicity, or patient refusal (whichever is first). All patients will be followed for survival up to 3 years from the first dose of the last patient enrolled in the study, or until death, end of the study, or patient withdrawal of consent, whichever comes first, regardless of initiation of new cancer therapy.

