9. DATA ANALYSIS/STATISTICAL METHODS

Detailed methodology for summary and statistical analyses of the data collected in this trial will be documented in a Statistical Analysis Plan (SAP), which will be maintained by Pfizer. The SAP may modify the plans outlined in the protocol; however, any major modifications of the primary endpoint definition and/or its analysis will also be reflected in a protocol amendment. Unless otherwise stated, the monotherapy cohort and the combination cohorts will be analyzed separately. The data from the Continuation Cohort will not be analyzed and will be presented in the form of patient data listings separately from the other cohorts.

The primary analysis will be performed after disease assessment on Cycle 9/Day 1 for the last (15th) patient treated in Expansion Cohort of LDAC combination for efficacy. The timing of the primary analysis is estimated to be after approximately 19 months after the first dose for the first patient in Expansion Cohort of LDAC combination for efficacy, assuming the enroll speed as 15 patients per year.

The final analysis will be performed after all patients have died or after the last patient last visit, whichever occurs first. Further analyses could be performed, if necessary.

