1. AMENDMENTS FROM PREVIOUS VERSION(S)

This Statistical Analysis Plan (SAP) v4 for study B1371005 is based on the protocol dated 21JAN2019 (protocol amendment 7) and the addition of the interim analysis. The analysis planned in SAP v4 will supersede the previous versions of the SAP and the statistical sections of the protocol.

Table 1. Summary of Major Changes in SAP Amendments

SAP Version	Change	Rationale
1	Not Applicable	Not Applicable
2	
 - Added the analysis plan of the 25 mg QD dose level in Monotherapy Cohort and amended the sample size of Monotherapy Cohort. - Added the analysis plan of the Combination Cohort 3. - Added the analysis plan of the Continuation Cohort. - Section 3 – Stated the timings of the primary and final analysis. - Section 6.1 – Added the definitions of the dates for the disease response. - Section 6.3.1 – Modified according to protocol amendment. - Section 7.4 – Conformed to Section 8.2.3.4 about analysis population. - Section 7.5 – Deleted the explanations of handlings of concentrations below/upper the limit of quantification. - Section 8.2.9.1.4 – Changed the definitions of the actual dose intensity and the relative dose intensities with reference to B1371003 - Section 8.2.9.1.4 – Added the listing of the actual dose intensity and the relative dose intensities with reference to B1371003 - Section 8.2.9.5 – Added the analysis plan of cytogenetics by European Leukemia Net. 	
 - Protocol amendment 3. - Protocol amendment 4. - Protocol amendment 5. - To clarify the timing of each analysis. - To include the dates related the efficacy as endpoints. - Protocol amendment 4. - Refer to Section 8.2.3.4. - Further amendment of SAP will be planned after investigation of handling of PD endpoints. - To unify the definition of these endpoints in Glasdegib program. - To unify the definition of these endpoints in Glasdegib program. - This characteristic is the prognostic factor for AML and will also be corrected in Phase 3 study for AML patients

	
 - Section 8.2.9.11 – Added the analysis plan of cardiac function evaluation - Section of Investigators Comments – This section was deleted 	
B1371019.
 
 - The analysis plan of this item was simply omitted. - This item is not included in analysis dataset.

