Treatment with PF-04449913 in combination with LDAC may continue for up to 12 cycles or until disease progression or relapse, patient refusal, or unacceptable toxicity occurs (whichever is first). Unfit patients who complete 12 cycles of study treatment will be deemed to have completed the study. However, patients who complete the 12 cycles of study treatment and demonstrate clinical benefit with manageable toxicity, and are willing to continue receiving the study treatment (monotherapy of PF-04449913 or combination therapy), may be given the opportunity to do so following agreement between the Investigator and Sponsor, and pending study drug availability. If treatment continues beyond 12 cycles, study procedures should continue to be performed as listed in Protocol Table 2 (Schedule of Activities). This cohort includes survival follow-up.

Expansion Cohort of LDAC Combination for Efficacy (Unfit Patients):

In this cohort, patients who are “unfit for intensive chemotherapy” based on predefined criteria (See Protocol Inclusion Criteria) will receive PF-04449913 once daily continuously in combination with LDAC over 28-day cycles.

A total of 15 patients will be treated and Disease Modifying Response (DMR) rate will be evaluated. Treatment with PF-04449913 in combination with LDAC may continue until disease progression or relapse, patient refusal, or unacceptable toxicity occurs (whichever is first). All patients will be followed for survival every 8 weeks up to 2 years from the first dose of the last patient enrolled in the study, or until death, end of the study, or patient withdrawal of consent, whichever comes first, regardless of initiation of new cancer therapy.

Combination Cohort 2 (Fit Patients):

In this cohort, patients defined as “fit for intensive chemotherapy” based on pre-defined criteria (See Protocol Inclusion Criteria) will receive PF-04449913 once daily continuously in combination with daunorubicin and cytarabine during induction and consolidation. For the first induction cycle only, PF-04449913 will commence on Day -3 and will then be given once daily continuously for the duration of treatment. Following completion of induction and consolidation, single-agent PF-04449913 may be given to eligible patients as maintenance therapy for a maximum of 6 cycles.

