Treatment will continue until disease progression or relapse, patient refusal, or unacceptable toxicity (whichever is first). Fit patients who complete induction, consolidation and 6 cycles of maintenance with PF-04449913 will be deemed to have completed the study treatment. However, patients who complete the 6 cycles of maintenance and demonstrate clinical benefit with manageable toxicity, and are willing to continue receiving single-agent PF-04449913, may be given the opportunity to do so following agreement between the Investigator and Sponsor, and pending study drug availability. If treatment continues beyond 6 cycles of maintenance, study procedures should continue to be performed as listed in Protocol Table 3 (Schedule of Activities).

Combination Cohort 3 (Azacitidine Combination):

In this cohort, patients with previously untreated AML and eligible for non-intensive chemotherapy will receive PF-04449913 once daily continuously at the starting dose of 100 mg in combination with azacitidine over 28 day cycles.

*Since responses to azacitidine may require 4-6 cycles of administration to emerge, treatment with the study drug combination should be continued for at least 6 cycles, or until death, unacceptable toxicity, or patient refusal (whichever is first). If documentation of disease progression occurs within the first 6 cycles of study treatment, the patient **SHOULD NOT** be withdrawn from study treatment following agreement between the Investigator and Sponsor if, in the Investigator's judgment, the patient is still likely to receive clinical benefit.*

Treatment with the study drug combination should be continued beyond 6 cycles of treatment until objective disease progression or relapse (unless according to the Investigator there is reasonable evidence of clinical benefit, eg, HI [hematologic improvement], to justify continuation on treatment following agreement between the Investigator and Sponsor), death, unacceptable toxicity, or patient refusal (whichever is first). All patients will be followed for survival up to 3 years from the first dose of the last patient enrolled in the study, or until death, end of the study, or patient withdrawal of consent, whichever comes first, regardless of initiation of new cancer therapy.

Continuation Cohort:

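### The SAP's 2-year final-analysis trigger conflicts with its own 3-year Cohort 3 survival follow-up and with the protocol's last-patient-last-visit trigger

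*SAP*

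**What the plan says.** SAP section 3 sets the final analysis "after all patients have died or 2 years after the first dose for the last patient treated, whichever occurs first". Since the earlier event governs, two years is a hard cap while any patient is alive. The section adds that further analyses may be done if needed, without a date or content.

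Protocol section 9 has a different rule: "The final analysis will be performed after all patients have died or after the last patient last visit, whichever occurs first". Protocol section 13 defines the end of trial as including the follow-up period.

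For Combination Cohort 3, SAP section 2.1 says that patients are "followed for survival up to 3 years from the first dose of the last patient enrolled in the study". The Protocol Summary gives the same horizon with a schedule, "followed for survival every 12 weeks up to 3 years from the first dose of the last patient enrolled in the study", and protocol sections 3.1.2 and 5.3.7 agree. Follow-up may end sooner at death, end of the study or withdrawal of consent.

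For the Expansion Cohort, SAP section 2.1 says "followed for survival every 8 weeks up to 2 years from the first dose of the last patient enrolled in the study". The current protocol, section 3.1.2, adds that "follow-up on survival status will no longer be required after Protocol Amendment 8".

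On precedence, SAP section 1 says that the planned analysis "will supersede the previous versions of the SAP and the statistical sections of the protocol". SAP v4 is based on Amendment 7, while the current protocol already carries Amendment 8 text.

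**The concern.** The plan has two definitions of the final analysis, and the shorter one sits in the document that claims precedence. It is also shorter than a follow-up window that the SAP itself states.

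Overall survival is a secondary endpoint in Cohort 3. SAP sections 8.2.2.2 and 8.2.2.4 plan Kaplan-Meier summaries of duration of response and survival there, with intervals for the 25th, 50th and 75th survival percentiles. If the SAP rule is applied, patients are asked to complete contacts that the planned final analysis does not use.

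Treatment is open-ended in Cohort 3 and the Expansion Cohort, and protocol section 8.2 records adverse events in both until 28 days after the last dose. Events in patients treated past the cut would therefore also fall outside it.

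The study is open-label. With two rules in force, the survival cut-off could be chosen after the data have been seen.

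**Working it through.** **The section's one derived timing figure.** SAP section 3 puts the primary analysis at about 19 months after the first Expansion Cohort dose. Accrual of 15 patients at 15 per year takes 12 months, and Cycle 9 Day 1 comes 8 × 28 = 224 days after the last first dose: 12 + 224/30.4375 = 12 + 7.36 = 19.4 months. This reproduces. The 2-year final trigger is a bare rule with no derivation.

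**Gap on the wording as written.** Both clocks start from the last patient in the study (treated in SAP section 3, enrolled in the Cohort 3 text). Gap = 36 − 24 = 12 months. At 12-weekly contacts that is 365.25/84 = 4.35, about four contacts per surviving patient. This is a maximum, because follow-up can end earlier.

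**Gap if the 3 years ran from the last Cohort 3 patient.** This is an assumption, not the wording. Let the lag L be the months from the last Cohort 3 first dose to the last first dose in the study. Gap = max(0, 12 − L).

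**Deaths in the gap.** Assumptions: exponential survival with the azacitidine median of 10.4 months cited in protocol section 1.2.4.3, 6 patients, and one common first-dose date for Cohort 3. S(t) = 0.5^(t/10.4). On the wording as written, expected deaths = 6 × [S(24 + L) − S(36 + L)].

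| Lag L (months) | S(24 + L) | S(36 + L) | Expected deaths in the gap | Gap on a per-cohort clock (months) |
|---|---|---|---|---|
| 0 | 0.202 | 0.091 | 6 × 0.111 = 0.67 | 12 |
| 12 | 0.091 | 0.041 | 6 × 0.050 = 0.30 | 0 |
| 18 | 0.061 | 0.027 | 6 × 0.034 = 0.20 | 0 |

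On a per-cohort clock with a lag of 12 months or more, the gap and its deaths are zero. At L = 0, about 6 × 0.202 = 1.2 patients would be alive at the cut.

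**Which lag is plausible.** Enrolment dates are not given. Amendment 4, which added Cohort 3, is dated 4 July 2017. Amendment 7, to which the SAP's change table ties the Expansion Cohort, is dated 21 January 2019. These are 18.6 months apart. Amendment dates are not enrolment dates, but they make L = 0 unlikely.

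**What lies before the cut.** The planned survival rates are at 6, 12 and 18 months, all below 24. Under the same model the median is 10.4 months and the 75th percentile is 2 × 10.4 = 20.8 months. A late percentile moves only if these six patients live longer than assumed.

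**The case against.** The best defence is version lag. SAP v4 was written for Amendment 7, and the available text does not show what that amendment said about the final analysis. The SAP trigger may have matched it then, and the precedence sentence is weak ground for overriding later protocol text. This stands for the difference between SAP and protocol. It does not explain the conflict inside the SAP, where section 2.1 keeps 3 years for Cohort 3 and section 3 stops at 2.

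A second defence is that a fixed calendar cut is legitimate. Last patient last visit across every cohort would tie the final analysis to open-ended treatment. That includes the single Continuation patient, who may be treated even past progression and whose data protocol section 9 reserves for listings. This stands as an argument about the remedy. It does not justify a cut shorter than a stated survival window with no reason given.

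A reader might infer that a year of required survival data is thrown away and late deaths and adverse events are never reported. The documents do not support that. SAP section 3 governs when data are analysed, not whether they are collected. The 3 years is an upper limit, and a later analysis is permitted. That permission is optional and undated, so it softens the problem without removing it.

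A reader might also infer that the Cohort 3 survival result is compromised. It is a descriptive result in six patients with no hypothesis attached, and protocol section 9.3 asks only for listings. All the planned survival rates fall before the cut.

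**Conclusion.** The inconsistency is real and minor. SAP section 3 cannot be reconciled with SAP section 2.1 for Cohort 3, and it differs from protocol section 9. The 2-year figure fits only an Expansion Cohort follow-up that is no longer required.

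Between 0 and 12 months of Cohort 3 survival follow-up fall outside the planned final analysis, depending on which patient starts the 3-year clock and on when follow-up actually ends. The expected number of deaths involved is about 0 to 0.7. The upper end needs Cohort 3 to have been first dosed together with the last study patient; at an assumed 18-month lag it is about 0.2. These counts rest on exponential survival with a 10.4-month median.

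What can change is the Kaplan-Meier tail, late percentiles and duration of response in 6 patients, and late safety data from patients still on treatment. The primary DMR test is untouched.

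**What to change.** Amend SAP section 3 in one of two ways:

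- Adopt the protocol's trigger of all patients dead or last patient last visit, and say that the Cohort 3 survival contacts count towards that last visit.
- Set a separate Cohort 3 survival cut-off at the end of its 3-year follow-up. This avoids tying the whole final analysis to open-ended treatment.

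In either case, state which patient starts each clock (the last in the study or the last in the cohort), exclude the listings-only Continuation patient from the trigger, and label any 2-year cut as an interim report. Update the SAP to the current protocol at the same time, so that the Expansion Cohort's discontinued survival follow-up no longer appears to support the 2-year figure.

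The cost is a sentence or two in the SAP and possibly a later final report. No new data collection is needed.
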